5.4 Inclusion/Exclusion Criteria

Inclusion Criteria

- Neurogenic bowel dysfunction using digital rectal stimulation
- Neurologically stable
- Skeletally mature
- Adults 18 years or greater
- Multiple Sclerosis or Stroke or Suprasacral SCI
- Must be past acute spinal shock phase

Exclusion Criteria

- Active sepsis
- Open pressure sores on or around pelvis
- Significant colon trauma or colostomy
- History of Autonomic Dysreflexia

5.5 Study Evaluations

Data collection will include standard medical charting and documenting outcome measures, such as bowel emptying time as written in section 5.6 Data Analysis. No tests, questionnaires, or procedures will be conducted beyond the typical bowel routine or stimulation testing described in this protocol.

5.6 Data Analysis

This work is considered a pilot study. Data will be collected to determine an effect size and power future studies that measure colonic motility in response to electrical stimulation. Therefore, 10 subjects are chosen to provide sufficient data to power a future study.

Bowel emptying will be performed by a trained clinician, caregiver, or subject (whoever normally performs it for the subject) using standard technique. The bowel routine is typically conducted with digital rectal stimulation and/or the insertion of suppositories or similar chemical systems. The time that elapses between initial intervention and bowel emptying will be measured as bowel emptying time. We will also test electrical stimulation to modulate an excitatory recto-colic reflex by stimulating via a rectal probe electrode. These systems are clinically available for chronic constipation in other indications and are considered minimal risk. We have experience measuring bowel activity with these methods. Initial introduction of the rectal probe electrode may cause temporary distension of the rectum. To ensure that reflexive activity due to the probe does not confound our data, we will wait approximately 5-10 minutes for the colon to relax back to baseline activity before beginning the bowel routine with stimulation.

The primary outcome variable is bowel emptying time. Bowel emptying time data are not expected to follow a normal distribution. Therefore, the non-parametric Mann-Whitney rank-sum test with a significance of 0.05 will be used to compare bowel emptying times between typical bowel routines and electrical stimulation conditions

across subjects. We expect to observe a great deal of variability in bowel emptying times, which may require many observations and subjects to achieve statistical significance.

Analysis on de-identified data will be performed by study staff. De-Identified data from this study may be pooled with data collected by [name] originating from a similar study of the same name currently approved at the Louis Stokes Cleveland DVA Medical Center.

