Electrical stimulation to evoke recto-colonic reflex for colonic motility

Funding Agency: VA RR&D

Principal Investigator: [name], DO

1593201-8/12-3-21/2021

Abstract

This study hopes to characterize the effects of minimally invasive electrical rectal stimulation on colonic motility in persons with neurogenic bowel dysfunction. Subjects will act as their own controls, with control data being obtained during subjects' typical bowel routines. Outcome measures include bowel emptying duration and amount of stool removed. These data will be compared to determine the efficacy of electrical stimulation to promote bowel emptying compared to patients' typical bowel routines, and to provide an effect size on the outcome measures of colonic motility for powering future studies.

We hypothesize that electrical rectal stimulation will produce increased colonic motility that results in defecation and that defecation time will be similar to subjects' typical bowel routines. The time required for defecation in response to their typical bowel routine and to minimally invasive electrical rectal stimulation will be monitored. Subjects will also be asked to report on sensations and comment on electrical stimulation.

List of Abbreviations

LSCDVAMC: Louis Stokes Cleveland DVA Medical Center

SVAMC: Syracuse VA Medical Center

SCI: spinal cord injury

EMG: electromyogram

AD: autonomic dysreflexia

NBD: neurogenic bowel dysfunction

FES: functional electrical stimulation

IRB: Institutional Review Board

Contents

1.0	Study Personnel	5
2.0	Introduction	5
3.0	Objectives	6
4.0	Resources and Personnel	6
5.0	Study Procedures	7
5.1	Study Design.....	7
5.2	Recruitment Methods	8
5.3	Informed Consent Procedures	9
5.4	Inclusion/Exclusion Criteria	9
5.5	Study Evaluations	10
5.6	Data Analysis.....	10
5.7	Withdrawal of Subjects	11
6.0	Reporting.....	11
7.0	Privacy and Confidentiality.....	11
8.0	References	12

Protocol Title: Electrical stimulation to evoke recto-colonic reflex for colonic motility

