3.0 Objectives

This pilot study hopes to characterize the effects of minimally invasive electrical rectal stimulation on colonic motility in persons with neurogenic bowel dysfunction, as well as collect data to determine an effect size and so power future studies that measure colonic motility in response to electrical stimulation

Our hypothesis is that electrical rectal stimulation will produce increased colonic motility that results in defecation and that defecation time will be similar to subjects' typical bowel routines.

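### Ten subjects are called sufficient to power a future study without a calculation, and the one specified method, an unpaired rank-sum test, gives neither a within-subject effect nor the variances a sample size needs

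*Combined protocol and SAP*

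**What the plan says.** Section 5.6 calls the work a pilot and gives its statistical purpose: "Data will be collected to determine an effect size and power future studies that measure colonic motility in response to electrical stimulation". It then concludes: "Therefore, 10 subjects are chosen to provide sufficient data to power a future study". The Abstract and section 3.0 state the same aim ("to provide an effect size on the outcome measures of colonic motility for powering future studies"; "collect data to determine an effect size and so power future studies").

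On method, section 5.6 says "The primary outcome variable is bowel emptying time" and that "the non-parametric Mann-Whitney rank-sum test with a significance of 0.05 will be used to compare bowel emptying times". No other analysis is specified. On variability it gives no figure, only "We expect to observe a great deal of variability in bowel emptying times", "which may require many observations and subjects to achieve statistical significance".

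The Abstract describes a within-subject comparison, with control data taken from each subject's usual bowel routine. Section 5.6 also allows de-identified data to be pooled with those of a similar study at another VA site, without giving that study's size.

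**The concern.** There are two gaps between the declared purpose and the plan.

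- **The number.** Sufficiency for powering a later study is a claim about precision. The plan gives no SD, target difference, margin, interval width, power or dropout allowance, so the claim can be neither reproduced nor checked.
- **The method.** A sample size for a later own-control study needs the within-subject effect, or a chosen difference or margin, together with the SD of the paired difference. The rank-sum test treats the two sets of times as independent and returns a p-value. As specified, it supplies none of these inputs.

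The study's main product, the planning information, is therefore undefined in the section that should define it. The wording also invites readers to treat estimates from 10 subjects as firm.

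**Working it through.** **1. Can 10 be reproduced?** No. Section 5.6 gives the number of subjects and the significance level and nothing else that a calculation would need. What can be computed is the precision that 10 subjects provide.

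**2. Inputs**
- n = 10 subjects (sections 5.1 and 5.6).
- Own-control design (Abstract), so one summary difference per subject and n − 1 = 9 degrees of freedom.
- Assumption: subject-level differences are approximately normal, possibly on the log scale. Section 5.6 expects the raw times not to be normal.
- No SD is given, so results are in SD units.

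**3. Precision of the SD.** The 95% limits for true SD / observed SD are √(9/χ²), with the 97.5% and 2.5% points of chi-square on 9 df (19.02 and 2.70):
- lower: √(9/19.02) = 0.69
- upper: √(9/2.70) = 1.83

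**4. Consequence for a future sample size.** For a fixed target difference or margin, N is proportional to SD², so the multipliers are squared:
- lower: 9/19.02 = 0.47
- upper: 9/2.70 = 3.33

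The ratio of the two is 19.02/2.70 = 7.0. This holds for a superiority, equivalence or non-inferiority design, because SD² enters the formula in the same way. It does not yet include any uncertainty in the mean.

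**5. Precision of the mean difference.** The 95% half-width in SD units is t(0.975, 9)/√10 = 2.262/3.162 = 0.715, about 0.72 SD.

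**6. Do repeated sessions help?** For subjects studied in two consecutive 6-week periods, every-other-day routines (section 5.1) give about 42/2 = 21 sessions per condition. At 3 to 5 a week (the description of typical routines) the range is 18 to 30. With m sessions per condition, and sessions independent within a subject, the variance of a subject's mean difference is

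σ²(between-subject effect) + 2σ²(within)/m.

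At m = 21 the second term is 2/21 = 0.095 of the within-subject variance, so session noise is much reduced. The first term does not shrink with m. The SD in steps 3 to 5 is the square root of the whole sum, and it is still estimated on 9 df. More sessions can make that SD smaller, but do not make its estimate relatively more precise.

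**7. If fewer subjects are evaluable.** The plan makes no allowance for loss. The same formulas give:

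| Evaluable subjects | SD limits (× observed) | Half-width (SD) |
|---|---|---|
| 10 | 0.69 to 1.83 | 0.72 |
| 8 | 0.66 to 2.04 | 0.84 |
| 7 | 0.64 to 2.20 | 0.92 |

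**The case against.** **It is a pilot, and it does intend an effect size.** Both are true. The Abstract and sections 3.0 and 5.6 all state the aim, and the raw emptying times will be there to compute differences and SDs. It would be wrong to say that the study seeks only a p-value. What is missing is the specification: estimator, scale, interval and variances. A shift estimate can accompany a rank-sum test, but none is named, and the usual one for this test would still ignore the pairing. Ten may well be reasonable on feasibility grounds, but section 5.6 justifies it by sufficiency for powering.

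**Pooling may add data.** It may. It is optional, its size is not stated, and it is not part of the argument for 10.

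**Section 5.6 already concedes high variability.** It does, and that sits awkwardly beside the claim of sufficiency.

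**Normality is assumed.** It is, against the plan's own expectation for the raw times. The precision figures need that condition attached.

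**Two stronger readings to avoid.**
- A reader might infer that, because the pilot has only 10 subjects, the next study is as likely as not to be underpowered. The documents do not say that it will be sized from a bare point estimate. The inference also does not turn on the number 10. With an assumed true standardised paired difference of 0.5 and planning from the pilot estimate, simulated true power falls below 80% in about 51% of cases with 10 pilot subjects and about 50% with 100. Only severe shortfall separates the two: power is below 50% in about 29% and 2% of cases.
- A reader might convert an assumed standardised effect and its interval into superiority sample sizes. No effect is given in the documents, and the hypothesis in section 3.0 is that emptying time will be similar under the two methods. A later study might therefore rest on a margin, where those numbers would not apply.

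**Conclusion.** The point holds in this form: the sufficiency claim in section 5.6 is unsupported, and the specified analysis does not deliver what the stated aim needs. With 10 subjects, an SD-based future sample size is uncertain from 0.47-fold to 3.3-fold, and the mean paired difference is known to about ±0.72 SD.

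These figures assume 10 evaluable subjects, one difference per subject and approximate normality on the scale chosen. They need no assumed effect size or future power. They do not show that 10 is the wrong number for a pilot, or that a future study will be underpowered. The matter should be corrected because it concerns the study's declared purpose. It does not concern subject safety.

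**What to change.** In section 5.6:

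1. Replace the sufficiency sentence with a feasibility justification for 10 subjects and a precision statement: 95% CI half-width about 0.72 SD of the paired difference, and true SD between 0.69 and 1.83 times the estimate. State the assumption of approximately normal subject-level differences on the chosen scale.
2. Make the primary deliverable the subject-level difference in bowel emptying time between conditions, with a 95% CI. Fix the scale in advance, for example a log-scale difference (reported as a ratio) or a median difference.
3. Report between-subject and within-subject SDs on that scale.
4. State that sample sizes for future studies will allow for the uncertainty in these estimates. The protocol need not commit a later study to a particular confidence limit.

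The cost is a change of wording, slightly more analysis and a less favourable precision claim. No extra subjects or procedures are needed.

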5.0 Study Procedures

5.1 Study Design

Experiments will be conducted in the SCI inpatient clinic in 10 individuals with neurogenic bowel dysfunction who have stable bowel routines. We will work with nursing staff on the study to maintain a consistent bowel emptying schedule for the subjects. We will not disrupt the patient's typical bowel emptying routine. Only the Research Nurse will be completing any research related procedures. Data will be collected from subjects over 6 weeks during their typical bowel routines. Then we will test minimally invasive electrical rectal stimulation via a rectal probe in a second 6-week period. Subjects will be instrumented with a rectal probe and stimulator inserted by the Research Nurse only for the duration of those bowel routines and effects are not expected to continue past the end of the experiment period. Subjects will return to their typical bowel routine at the end of the 6-week stimulation testing period. For patients >6 months post-SCI, the control period for the study will consist of their typical digital stim bowel routine. Nurses will log dig stim data as they usually do and this data will be used as control data for the study. During the experimental phase of the experiment, dig stim will be replaced with electrical stimulation. Use of electrical stim will not change the patients' bowel routine otherwise. There is no set schedule for the intervention because we are adapting to each patients' normal bowel routine. The only structure is that we have a defined control period using their normal routine, followed by a defined experimental period with the electrical stimulation. For a normal bowel routine, patients typically receive bowel intervention every other day in a typical week.

For subjects within 6 months of SCI diagnosis, but after the acute spinal shock phase, we will instead alternate between periods of control intervention (dig stim) and electrical stimulation. This will be done 3-7 times a week to optimize data acquisition, rather than having a defined control period followed by a defined experimental period. Neither the altered procedure nor the inclusion of patients who are <6 months post-SCI will affect the risk level of the study. Acute spinal shock is defined as the period immediately following an acute spinal cord injury. This phase resolves 72 hours post-injury and it is exceptionally rare that a patient in this phase of injury would be in the SCI, rather than the ICU.

Typical Bowel Routine

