
Typical bowel routines usually involve digital rectal stimulation conducted by the subject, their nurse, or their caregiver. An individual inserts a gloved finger through the anus into the rectum and mechanically distends the rectum by moving back and forth against the inside of the rectal wall for approximately 30 seconds. Time is allowed for the colon to move and evacuate some stools, then the process is repeated (typically 15-20 minutes later). Digital rectal stimulation is thus repeated until the colon contents are empty, usually marked by the appearance of mucus and no evidence of stools in the distal colon or rectum. Some subjects may also receive a mini-enema or other

suppository to aid in bowel emptying. Individual bowel routine schedules vary but are typically conducted 3-5 times a week.

Electrical Rectal Stimulation

A clinically standard rectal probe electrode will be inserted into the rectum to administer electrical stimulation. The probe electrode will only be in place to administer bouts of stimulation just as gloved fingers administer digital rectal distension, after which it will be removed to allow for bowel emptying. The probe electrode will be connected to a Digitimer stimulator DS7A, which is FDA-approved for electrical stimulation in human subjects and has been used in our previous, similar experiments for bladder function. Stimulation will either be 20 Hz constant frequency or burst pattern stimulation delivered as 5-50 pulses at 100-200 Hz once per second. We will first determine the stimulation amplitudes at which the subject can sense stimulation and at what limit they tolerate stimulation but do not wish to go higher for concern of discomfort. We will then apply stimulation within this range, not expected to exceed 40 mA, which is the typical range we see in similar applications of surface electrical stimulation. Stimulation will be administered continuously for the duration of the bowel routine. If stimulation does not increase colonic motility and promote defecation, as determined by each subject's baseline data on bowel emptying time, nurse experience, or clinician expertise, then we will cease stimulation for that day and return to the subject's typical bowel routine. If stimulation fails to increase colonic motility for bowel emptying on 3 or more occasions in a given subject, then we will stop the 6-week stimulation period and return that subject to their typical bowel routine.

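### The primary Mann-Whitney test is unpaired, but each subject is their own control and gives repeated sessions under both conditions, so the 0.05 level is not controlled and the pairing is lost

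*Combined protocol and SAP*

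**What the plan says.** The Abstract sets a within-subject design: "Subjects will act as their own controls, with control data being obtained during subjects' typical bowel routines". Section 5.1 gives subjects more than 6 months post-injury two consecutive blocks: "Data will be collected from subjects over 6 weeks during their typical bowel routines", and "Then we will test minimally invasive electrical rectal stimulation via a rectal probe in a second 6-week period". On frequency it says that "patients typically receive bowel intervention every other day in a typical week" and, under Typical Bowel Routine, "Individual bowel routine schedules vary but are typically conducted 3-5 times a week". Subjects less than 6 months post-injury alternate between the two conditions at 3 to 7 sessions a week; no total duration is given for them.

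In section 5.6, "The primary outcome variable is bowel emptying time", and the "Mann-Whitney rank-sum test with a significance of 0.05 will be used to compare bowel emptying times between typical bowel routines and electrical stimulation conditions", a comparison made across subjects. Expected non-normality is the only reason given for the test. The sample size statement is that "10 subjects are chosen to provide sufficient data to power a future study". Nowhere do the documents mention a paired test, a per-subject summary, a mixed model, or any handling of repeated sessions or unequal session counts.

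**The concern.** Non-normality is a reason to use a rank test. It is not a reason to use an unpaired one. The Mann-Whitney test assumes that the two samples are independent of each other and that observations within each are independent. Neither holds when the same 10 people give repeated sessions to both samples.

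The stated test can be run in two ways, and both go wrong:

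- **All sessions pooled** (about 210 versus 210). Repeated sessions of one person count as independent, variation between people in their response is ignored, and people with more sessions carry more weight.
- **One value per subject** (10 versus 10). The spread between subjects stays in the error term, although the design was chosen to remove it.

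Two things are at stake: the p-value for the primary outcome, and the pilot's own product. A future own-control study is sized from the SD of within-subject differences, and an unpaired analysis does not deliver that quantity.

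**Working it through.** **Inputs from the documents.** 10 subjects (5.6); level 0.05, sidedness not stated and taken as two-sided (5.6); two 6-week periods (5.1). Sessions per condition follow by arithmetic: 42 days / 2 = 21 if every other day; 6 × 3 = 18 to 6 × 5 = 30 at 3 to 5 a week. Pooled, that is 10 × 21 = 210 per condition. For the alternating subjects the number cannot be derived.

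**Assumptions.** The documents give no variance components. Set the total variance to 1 and split it into a stable subject share *s*, a subject-by-condition share *g*, and session noise 1 − *s* − *g*. Each setting has 2,000 simulated trials, so the Monte Carlo standard error is √(0.05 × 0.95 / 2000) ≈ 0.5 points at 5%.

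**Step 1: reproduce the plan's 0.05.** With fully independent observations (*s* = *g* = 0) the pooled test rejects 6.0% and the 10 versus 10 test 5.0%. The nominal level is recovered, approximately, only without clustering or pairing.

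**Step 2: no average effect, 21 sessions per condition (% rejecting).**

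| *s* | *g* | Pooled sessions | 10 v 10 medians, unpaired | Signed-rank on subject differences |
|---|---|---|---|---|
| 0.3 | 0 | 2.9 | 0.0 | 5.5 |
| 0.5 | 0 | 1.2 | 0.0 | 5.5 |
| 0.7 | 0 | 0.3 | 0.0 | 5.5 |
| 0.5 | 0.02 | 4.4 | 0.0 | 5.1 |
| 0.5 | 0.05 | 11.9 | 0.0 | 4.8 |
| 0.5 | 0.10 | 22.5 | 0.1 | 4.3 |
| 0.5 | 0.20 | 36.9 | 0.1 | 4.5 |
| 0.3 | 0.05 | 13.1 | 0.2 | 4.8 |
| 0.3 | 0.20 | 37.0 | 0.5 | 4.4 |

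For *s* = 0.5, *g* = 0.05, the pooled rate is 9.9% with 18 sessions and 17.7% with 30.

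**Step 3: analytic check of the pooled column.** With *m* sessions per condition, the true variance of the pooled difference divided by the variance that the test assumes is about (1 − *s* − *g*) + *m·g*. The error rate is then about 2[1 − Φ(1.96/√ratio)].

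- *s* = 0.5, *g* = 0: ratio 0.5, rate 0.6%.
- *s* = 0.5, *g* = 0.05: 0.45 + 21 × 0.05 = 1.5, rate 11.0%.
- *s* = 0.5, *g* = 0.10: 0.40 + 21 × 0.10 = 2.5, rate 21.5%.

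The ratio equals 1 only when *g* = *s*/(*m* − 1), here 0.5/20 = 0.025. Below that the pooled test is conservative; above it, liberal. The plan has no means of knowing which side it is on.

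**Step 4: why the 10 versus 10 test almost never rejects.** Using means for simplicity, with *s* = 0.5 and *g* = 0.05, the variance that matters per subject and condition is 0.05 + 0.45/21 = 0.071. The unpaired test works with 0.071 + 0.5 = 0.571, so the ratio is 0.125.

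**Step 5: unequal session counts.** Section 5.1 ends a subject's stimulation period after 3 or more failures, so a subject could give as few as 3 stimulation sessions against about 21 control sessions. If 3 of 10 subjects do so, the pooled test rejects 11.4% (*s* = 0.3) or 14.2% (*s* = 0.5) even with *g* = 0. The signed-rank test stays at 5.1%.

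**Step 6: log-normal times.** Assume log-scale SDs of 0.3 to 0.5 between subjects and 0.4 between sessions, with a separate SD for how subjects differ in response. With no average effect the pooled test rejects 0.4 to 2% (response SD 0), 11 to 19% (0.2) and 22 to 31% (0.3). The 10 versus 10 test rejects under 1%, and the signed-rank test 4 to 6%. For a true 25% longer time at response SD 0.2, power is 2 to 16% for the 10 versus 10 test and about 69% for the signed-rank test.

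**The case against.** The best defence is that this is a pilot meant to supply an effect size, with no decision tied to p < 0.05, and that section 5.6 itself warns that significance may need more observations and subjects. The magnitudes also rest on assumed variances. At response SD 0.1 the pooled test rejects 2 to 7%, close to nominal. With a shared subject effect alone and equal counts it is conservative. With a session SD of 0.8 instead of 0.4, inflation at response SD 0.2 is 9 to 10%, and signed-rank power drops to about 38 to 39%. The pooled test also has high apparent power, about 90 to 95% in the 25% setting, although without error control that figure means little.

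Much of this stands as qualification. The supportable statement is that the error rate is not controlled, not that it is inflated. The figure of about 21 sessions is derived and applies only to subjects more than 6 months post-injury.

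The pilot argument does not rescue the test. The plan still commits to a 0.05 test of its primary outcome, and the planning purpose makes the loss of the within-subject variance more serious, not less.

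**Conclusion.** The concern holds. The stated test contradicts the stated design on either reading, and nothing elsewhere in the documents repairs it. Under the assumed variances, the real error rate of the nominal 5% test runs from 0.3% to 37% when sessions are pooled, and is 0.5% or less when one value per subject is compared unpaired. A paired analysis of the same data holds 4 to 6%. In the second reading, power for an assumed 25% effect falls from about 69% to between 2 and 16%. These sizes are illustrative and the direction for the pooled reading is unknown in advance. The mismatch itself depends on no assumption.

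**What to change.** Replace the Mann-Whitney sentence in section 5.6.

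- **Primary analysis:** for each subject, take the median log bowel emptying time under stimulation minus that under control. Test the 10 differences with the Wilcoxon signed-rank test, two-sided at 0.05. Report the Hodges-Lehmann estimate with its 95% CI, back-transformed to a ratio of times.
- **Supportive analysis:** a mixed model on log time, with condition and schedule cohort (fixed-order or alternating) as fixed effects, a random subject intercept and a random subject-by-condition slope. It supplies the variance components for the next study. With 10 subjects the fit may be unstable, so it should not be primary.
- **Data rule:** state in advance how a session that was returned to the typical routine enters a subject's median. Any analysis of this outcome needs that rule.

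The change to the test is a rewording of one paragraph; it needs no extra data, subjects or visits. It does not remove order effects in the fixed-order cohort, and a difference test does not establish the similarity in section 3.0's hypothesis. Those are separate points, although the confidence interval is more informative about similarity than a p-value.

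### The primary Mann-Whitney test assumes independent samples although each subject supplies repeated sessions under both conditions, and the unit of analysis is not fixed, so the 5% level is not assured

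*Combined protocol and SAP*

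**What the plan says.** The Abstract sets out a within-subject design: "Subjects will act as their own controls, with control data being obtained during subjects' typical bowel routines". Section 5.1 applies this to both patient groups. Subjects more than 6 months after injury have six weeks of their usual routine and then six weeks of stimulation: "During the experimental phase of the experiment, dig stim will be replaced with electrical stimulation". For those within 6 months, the plan is that "we will instead alternate between periods of control intervention (dig stim) and electrical stimulation". Either way, each subject gives many timed sessions under each condition.

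Section 5.6 makes bowel emptying time the primary outcome and defines it: "The time that elapses between initial intervention and bowel emptying will be measured as bowel emptying time". The analysis is that the "Mann-Whitney rank-sum test with a significance of 0.05 will be used to compare bowel emptying times between typical bowel routines" and stimulation, and the sentence continues "across subjects. We expect to observe a great deal of variability in bowel emptying times, which may require many observations and subjects". The only reason given for the test is that the times are not expected to be normal. No section mentions pairing, a per-subject summary, a mixed model or an allowance for clustering.

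Under Electrical Rectal Stimulation in section 5.1, a session in which stimulation does not work reverts to the usual routine that day. Three or more such failures end that subject's stimulation period.

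**The concern.** Non-normality is a reason to use ranks. It is not a reason to ignore pairing. The wording of section 5.6 allows two units of analysis, and the test fits neither:

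- **Session.** Times from one subject are correlated but are treated as independent. The early-stop rule can also leave a subject with a full set of control times and few stimulation times.
- **Subject.** With one value per subject and condition, an unpaired test puts back the between-subject variation that self-control is meant to remove.

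This is the study's main p-value. Section 3.0 hypothesises that "defecation time will be similar to subjects' typical bowel routines", so a non-significant result from a low-powered test could be misread as support. The pilot is also meant to supply an effect size for a later study. Section 5.6 does not define one, and an unpaired comparison does not give the within-subject contrast that the later study would need.

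**Working it through.** **Inputs from the documents.** 10 subjects; six weeks per condition; sessions typically every other day, so 42/2 = 21 per condition (section 5.1). The description of the typical routine gives 3-5 a week, so 6 × 3 = 18 to 6 × 5 = 30. Significance level 0.05 (section 5.6); two-sided is assumed because the section does not say.

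**Assumed, because the documents give no variances.** Normal times on a transformed scale, with between-subject plus residual variance 1. ICC (the between-subject share) is 0.3, 0.5 or 0.7. The effect varies between subjects with SD τ = 0, 0.25 or 0.5. All subjects have 21 sessions per condition, although no count is stated for those who alternate.

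**Step 1: the plan's own figure.** With zero within-subject correlation, simulation returns the nominal 5%: 0.051 for pooled sessions, 0.051 for unpaired subject medians and 0.051 for the signed-rank test.

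**Step 2: pooled sessions, no early stops.** A check using means shows the mechanism. With n = 10 and m = 21:

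- true variance of the difference = τ²/n + 2(1 − ICC)/(nm)
- variance assumed under independence = (2 + τ²)/(nm)

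At ICC 0.5 and τ = 0: true 1/210 = 0.0048, assumed 2/210 = 0.0095, ratio 0.50. The effective cut-off is 1.96/√0.50 = 2.77, so rejection is about 0.6%.

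At ICC 0.5 and τ = 0.5: true 0.025 + 0.0048 = 0.0298, assumed 2.25/210 = 0.0107, ratio 2.78. The cut-off is 1.96/√2.78 = 1.18, so rejection is about 24%.

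The two variances are equal when τ² = 2·ICC/(m − 1) = ICC/10, that is τ = 0.17, 0.22 and 0.26 at ICC 0.3, 0.5 and 0.7. There the test happens to hold its level.

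Simulation of the Mann-Whitney test itself agrees (2,000 runs per cell, no average effect, range over ICC):

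| Effect SD τ | Pooled sessions, rejection |
|---|---|
| 0 | 0.3-2.3% |
| 0.25 | 5.9-10.2% |
| 0.5 | 24.4-26.3% |

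Independent reruns widen the outer rows to about 0-3% and 22-26%. In between, rejection was 4.9% (ICC 0.3, τ 0.15), 5.0% (ICC 0.5, τ 0.2) and 3.6% (ICC 0.7, τ 0.2).

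**Step 3: pooled sessions with early stops.** The result depends on how the stop rule is modelled:

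- *Extreme case.* Three random subjects cut to exactly three stimulation sessions: about 8-20% at τ = 0.
- *Outcome-based rule.* A failure is a time above the subject's own control 95th percentile, and the subject stops at the third. This gives about three stops per 10 subjects, with rejection about 3-5% at τ = 0 and 11-13% at τ = 0.25.

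**Step 4: one median per subject, no early stops.**

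| | Unpaired Mann-Whitney | Signed-rank |
|---|---|---|
| Rejection, no average effect | about 0-1% | about 4-6% |
| Power, 0.5 SD shift | about 6-38% | 63-100% |

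At a 1 SD shift the unpaired test has power 66-98%.

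**Step 5: can the signed-rank test reach significance?** The smallest exact two-sided p is 2/2ⁿ: 2/1024 = 0.002 for n = 10, 2/64 = 0.031 for n = 6 and 2/32 = 0.0625 for n = 5. At least six subjects with both conditions are needed.

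**The case against.** Four points on the other side have weight.

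- **The p-value need not be wrong.** A reader might infer that it is wrong in every case, or that false positives are inflated. The documents support neither. On pooled sessions the error can go either way and can land on 5%; on subject medians the test is conservative. What stands is that nothing in the plan secures the level.
- **Early stopping need not cause large inflation.** A reader might take 8-20% as the effect of the stop rule. That figure assumes the earliest possible stop. Failures may accumulate at any point in the six weeks and depend on outcome, and the stricter outcome-based version gave about 3-5% at uniform effect.
- **A real difference would not usually be missed.** That inference holds only for moderate shifts. The documents give no expected difference, and a 1 SD shift would usually be found even unpaired.
- **This is a 10-subject pilot.** Section 5.6 already warns that significance may need more data, and a within-subject estimate can still be computed from what is collected. This limits the consequence, but the section still names a primary test at 0.05 that does not match the design.

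The signed-rank test is not immune either. With a looser failure threshold (control 80th percentile, about seven stops per 10 subjects), it rejected 5-8% at ICC 0.3 and 0.5.

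Separate Mann-Whitney tests within each subject would be closer to valid, but section 5.6 describes a comparison across subjects.

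**Conclusion.** The point holds. The named test does not match the self-controlled, repeated-session design, the unit is not fixed, and the nominal 5% is not guaranteed on either reading. For pooled sessions the documents fix neither the direction nor the size of the error: 0-3% to 22-26% without stops is a range over assumed ICC and effect variation, not an estimate. For unpaired medians the direction is clear over the ICC range assumed: very conservative, with weak power at 0.5 SD. The core contrast, with the signed-rank test near 5% and the Mann-Whitney test either unpredictable or very conservative, recurred in independent simulations. Because this is a pilot and the data still allow the right analysis, the change should be made before analysis, but the defect does not threaten the study itself.

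**What to change.** In section 5.6, replace the Mann-Whitney test with the following:

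- For each subject, take the median emptying time under stimulation minus the median under the typical routine. Test these differences with the Wilcoxon signed-rank test, two-sided at 0.05.
- Report the Hodges-Lehmann estimate of the difference with its 95% CI as the pilot effect size. Judge similarity from that CI, not from p > 0.05.
- Keep sessions that revert to the usual routine in the stimulation condition, timed from the start of stimulation. This follows the section's own definition of emptying time.
- Keep subjects whose stimulation period is ended for repeated failure, using the stimulation sessions they had. Report session counts per subject and condition.

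The cost is a few sentences and no extra subjects. The session log must show when stimulation began and whether the session reverted. The downside is that the subject becomes the unit (10 here, more if the Cleveland data are pooled), so nominal precision is lower than with pooled sessions. A stopped subject's median may also rest on as few as three sessions.
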